12.4.5 Sensitivity analyses for primary endpoint/estimand

The lower level of CTS will be used to verify positivity or negativity for the sensitivity analysis. For instance, if pathology (CTS Level 1) is used as true standard for primary estimand, imaging component of CTS (Level 2) will be used as true standard for sensitivity analysis for primary estimand. However, for those using changes in PSA level (CTS Level 3) as the true standard for primary estimand, their positivity status cannot be replaced by another component of CTS for sensitivity analysis.

Supplementary analysis 12.4.6

As supplementary analyses performed in the EFF, the region-level CLR and patient-level PPV and 95% CIs will be obtained from covariate adjusted logistic regression model. Important covariate will be specified in the SAP.

Subgroup analyses for region-level CLR and patient-level PPV will be performed:

patients with prior radical prostatectomy

patients with prior curative intent radiation therapy

If the co-primary endpoints are met, other subgroup analyses to assess the homogeneity of the treatment effect across demographic and baseline disease characteristics will be performed. Other subgroups will be specified in the SAP. Further supplementary analyses will be specified in the SAP.

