## 2.5.2 Statistical hypothesis, model, and method of analysis

For region-level CLR, the observations (regions positive/negative status) are clustered within a participant. Observations within participants (clusters) are correlated, which may lead to biased estimates of region-level CLR when the correlated nature of the data within each cluster is ignored. More important, an analysis ignoring correlation often yields a misleading small estimated standard error (and 95% CI) for CLR because it erroneously counts all observations as independent observations. Region-level CLR adjusted for correlation among observations within participants can be modeled by using a logistic regression model with random effects (Gatsonis CA 1995, Verbeke G, Molenberghs G 2000).

When calculating CLR, the number of TP regions  $(y_i)$ , follows the binomial distribution with parameter  $(n_i, p_i)$ ,

$$y_i|b_i\sim \text{Binomial}(n_i,p_i)$$

 $p_i$  denotes the probability of TP among all positive PET regions (TP or FP) for participant i, and  $n_i$  corresponds to the denominator in the CLR definition, i.e. the number of all regions containing at least one PET-positive finding by central assessments (TP or FP regions) for participant i.

The number of TP and FP regions overall (i.e. across all five regions, which are prostate region, PLN, skeletal, extra-pelvic lymph nodes and visceral) and by region across all participants in the EFF will be presented, along with region-level CLR and two-sided 95% CIs estimated using the following logistic regression model with random effects.

$$\log\left(\frac{p_i}{1-p_i}\right) = \mu + b_i$$

where  $p_i$  is the region-level CLR for participant i,  $\mu$  is the fixed effect of overall mean,  $b_i$  is the random effect for participants (clusters).  $b_i$  follows a normal distribution:  $b_i \sim N(0, \sigma_h^2)$ .

The lower bound of the 95% CI should be greater than 0.50 to attain the first co-primary endpoint.

**For patient-level PPV**, the number of TP and FP participants, as well as the number of positive and negative (and inconclusive, if applicable) [F]CTT1057 PET/CT scans, will be presented, along with patient-level PPV with two-sided exact binomial 95% CIs (Clopper and Pearson 1934).

The lower bound of the 95% CI for patient-level PPV should be greater than 0.20 attain the second co-primary endpoint.

The same analysis for patient-level PPV will be repeated by CTS Level.

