#### 2.5.6 Supplementary analyses

Supplementary analyses for region-level CLR and patient-level PPV will be performed for the following subgroups:

- Initial definitive therapy received:
  - o prior radical prostatectomy
  - o prior curative intent radiation therapy
- PSA level at baseline (from central laboratory):

- $PSA \le 0.5 \text{ ng/mL}$
- $\circ$  0.5 ng/mL<PSA $\leq$ 1 ng/mL
- $\circ$  1 ng/mL<PSA $\leq$ 2 ng/mL
- $\circ$  2 ng/mL<PSA $\leq$ 5 ng/mL
- $\circ$  PSA > 5 ng/mL

In addition, estimates of region-level CLR and corresponding 95% CI will be obtained from the logistic random-effects regression model, adjusting for covariates and taking into account the correlation among regions within one participant; while estimates of patient-level PPV and corresponding 95% CI will be obtained from the logistic regression model adjusting for covariates. Candidate covariates include categorized PSA level at baseline (from central laboratory) and the initial definitive therapy received (with either RP or curative-intent RT) as given above. The p-values from the Type III tests for each candidate covariate in the full model will be provided. The region-level CLR and patient-level PPV (and their 95% CIs) for each level of the covariates estimated from the full model including all candidate covariates, as well as the final model including only statistically significant covariates (p-value < 0.05), will be displayed. In the case there are no statistically significant covariates identified from the full model, the region-level CLR (and 95% CI) from the unadjusted logistic regression model and the patient-level PPV (and 95% CI) from the unadjusted logistic regression model will be provided.

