#### **Region-level CLR**

Correlated binary test results occur in this situation where each experimental unit (participant) consists of five correlated regions. Lee and Dubin developed a sample size formula for clustered binary data (Lee and Dubin 1994). They propose estimating the binary proportion by assigning equal weights to clusters regardless of their sizes to simplify the derivation of their sample size

formula. The weighted estimator for region-level CLR is approximately Gaussian distributed with a variance of a beta distribution (beta-binomial model).

The null hypothesis (H0: region-level CLR p = 0.50) will be tested against the alternative hypothesis (H1: p > 0.50). Assuming a CLR of 0.58 under the alternative hypothesis, a total sample size of 172 enrolled participants would achieve 90% statistical power to detect a change in CLR of 0.08 using a one-sided test at a target significance level of 2.5%. This sample size includes an adjustment for a dropout rate of 20%.

The sample size was determined as n to ensure a type I error using a one-sided significance level of 2.5% and with 90% power to reject H0 if the alternative H1 is true.

By the standard normal approximation, the sample size is given as follows:

$$n = \frac{\sigma^2 (Z_{\alpha} - Z_{1-\beta})^2}{(p_1 - p_0)^2}$$

where  $\sigma^2$  is the variance of a beta distribution,  $Z_a$  is the upper quantile of the standard normal distribution,  $p_0$  is a CLR of 0.50 under the null hypothesis, and  $p_1$  is a CLR of 0.58 under the alternative hypothesis.

Suppose there is no information on the within-cluster correlation of test results. In this case, a uniform distribution seems reasonable, setting parameters in the beta distribution of alpha=1 and beta=1. Then  $\sigma^2$  is 1/12.

Under these assumptions, 137 participants will be necessary to ensure 90% power. Taking into account a 20% dropout rate, a total of 172 participants will be recruited for this endpoint of the study.

The lower bound of the 95% CI for CRL should be greater than 0.50 to be considered a success.

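### Read literally, the fallback in SAP 2.5.6 drops the participant random effect from region-level CLR, which would make that supplementary 95% CI too narrow

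*SAP*

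**What the plan says.** SAP 2.5.6 names two different models for the covariate-adjusted supplementary analyses. Region-level CLR estimates "will be obtained from the logistic random-effects regression model, adjusting for covariates and taking into account the correlation among regions within one participant". Patient-level PPV estimates "will be obtained from the logistic regression model adjusting for covariates", which is enough there because each participant contributes one observation.

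The paragraph then describes a full model, a final model with significant covariates only, and a fallback. The fallback begins "In the case there are no statistically significant covariates identified from the full model" and calls for "the region-level CLR (and 95% CI) from the unadjusted logistic regression model and the patient-level PPV" from an unadjusted logistic regression as well. The two endpoints now share one model name, and no random effect is mentioned for CLR.

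Elsewhere the plan is consistent about clustering:
- SAP 1.2.1 (primary estimand 1) requires logistic random-effects models for the CLR summary measure.
- SAP 2.5.2 states: "Region-level CLR adjusted for correlation among observations within participants can be modeled by using a logistic regression model with random effects". It also warns that "an analysis ignoring correlation often yields a misleading small estimated standard error (and 95% CI) for CLR".
- SAP 3.1 sizes the trial on the basis that "Correlated binary test results occur in this situation where each experimental unit (participant) consists of five correlated regions".
- SAP 5.4.1 implements CLR in GLIMMIX with a random intercept per participant.

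Protocol 12.4.6 uses one label for both endpoints: "the region-level CLR and patient-level PPV and 95% CIs will be obtained from covariate adjusted logistic regression model".

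**The concern.** Removing covariates does not remove clustering. If a programmer follows the fallback as worded and fits an intercept-only logistic regression to the regions, every PET-positive region counts as an independent observation. That is the error SAP 2.5.2 warns against.

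The report would then carry, for each central reader, a supplementary CLR interval narrower than the data justify. Its lower bound could lie above 0.50 when the primary lower bound does not.

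The plain model also has a different target. It estimates a marginal proportion, whereas SAP 5.4.1 reports the subject-specific CLR at a random effect of zero. The two results would not be directly comparable even though both would be labelled unadjusted.

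**Working it through.** **1. The plan's own figures (SAP 3.1).** With σ² = 1/12 from Beta(1,1), one-sided 2.5%, 90% power, p₀ = 0.50 and p₁ = 0.58:
- n = (1/12)(1.960 + 1.282)² / 0.08² = 136.8, so 137.
- 137 / 0.8 = 171.25, so 172 enrolled.
- Power at 152 evaluable = Φ(0.08 / √((1/12)/152) − 1.96) = 92.7%.

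All three match the documents.

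**2. Inputs for the check.**
- Between-participant distribution Beta(1,1) (SAP 3.1). This implies ICC = 1/(1 + 1 + 1) = 1/3.
- PET-positive participants: 152 × 0.80 = 121.6, about 122 (SAP 3 and 3.1).
- PET-positive regions per positive participant, n: **not given in the documents**. All values below are assumptions.

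**3. Formulas.** Design effect D = 1 + (E[n²]/E[n] − 1) × ICC. A nominal 95% CI that ignores clustering has coverage of about 2Φ(1.96/√D) − 1. At a true CLR of 0.50, its lower bound exceeds 0.50 with probability of about Φ(−1.96/√D).

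Worked example, with an assumed mix of 1 to 5 positive regions in 50/25/13/8/4% of participants:
- E[n] = 1.91, E[n²] = 4.95, ratio 2.59.
- D = 1 + 1.59/3 = 1.53 and 1.96/√1.53 = 1.58.
- Coverage 88.7%, upper-side error 5.7%.

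**4. Results at ICC 1/3, true CLR 0.50, plain logistic model.**

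| Assumed positive regions | D | Coverage (formula) | Lower bound > 0.50 (formula) | Simulated coverage; error |
|---|---|---|---|---|
| One each | 1.00 | 95.0% | 2.5% | – |
| Mix 70/20/7/2/1%, mean 1.44 | 1.29 | 91.5% | 4.2% | – |
| Two each | 1.33 | 91.0% | 4.5% | 91.3–91.4%; 4.2–4.4% |
| Mix 50/25/13/8/4%, mean 1.91 | 1.53 | 88.7% | 5.7% | 88.9–89.1%; 5.3–5.6% |
| Three each | 1.67 | 87.1% | 6.4% | 86.5–86.6%; 6.5–6.8% |
| Five each (extreme) | 2.33 | 80.1% | 10.0% | 80.4%; 9.7% |

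The simulations are beta-binomial with 122 participants and 20,000 replicates. A random-intercept logistic model gave 1.9–2.6% in the four simulated settings, and a cluster-robust interval gave 2.4–2.7%. The excess therefore comes from ignoring the clustering.

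**5. Sensitivity to the ICC.**
- ICC 0.1, mean-1.91 mix: D = 1.16, coverage 93.1%, error 3.4%.
- ICC 0.05, same mix: D = 1.08, coverage 94.1%, error 3.0%.
- ICC 0.5: simulated coverage runs from about 75% (five each) to about 90% (two each).

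**6. Effect at the design alternative.** Take an observed CLR of 0.58, 122 participants and two regions each.
- The plain standard error is √(0.58 × 0.42 / 244) = 0.0316, so the lower bound is 0.518.
- Multiplying the standard error by √1.33 = 1.155 moves the lower bound to 0.509.
- With the mean-1.91 mix and a true CLR of 0.58, the plain model clears 0.50 in 65% of simulated trials and the random-intercept model in 53%.

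**The case against.** The strongest reply is that this is a wording slip. *Unadjusted* most naturally means the same model without covariates. The sentence names a model separately for each endpoint, which would be needless if both used one model. The SAP's document history describes the added text as display instructions for the covariate-adjusted logistic (random-effects) model. SAP 5.4.1 refers CLR to Section 2.5, which contains 2.5.6, and gives random-intercept code only. A programmer would probably fit the right model. This stands as an account of intent, so a reader should not infer that the sponsor deliberately chose a model without a random effect. It does not remove the problem, because no sentence says that the fallback is the 2.5.2 model, and the name used is the one the same paragraph reserves for PPV.

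The size can also be overstated. A reader might take the five-region figures as the expected effect because SAP 3.1 describes five regions per participant. That is the anatomical division; the CLR denominator in SAP 2.5.2 counts PET-positive regions only. ICC 1/3 is itself a default, adopted in SAP 3.1 for want of information on the correlation. Using the SAP's default estimator (RSPL) with the mean-1.91 mix, 600 simulated trials gave 6.8% for the plain model against 2.5% at ICC 1/3, but only 3.0% against 2.2% at ICC 0.1.

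Protocol 12.4.6 adds little. A random-effects logistic model is a logistic regression model, and the protocol leaves the details to the SAP. Finally, the report will still contain the primary random-effects interval and the weighted-estimator interval of SAP 2.5.5, so a fallback interval that is too narrow could be noticed.

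**Conclusion.** The point holds as a defect of wording with a real statistical consequence if followed. As written, the fallback contradicts SAP 1.2.1, 2.5.2 and 5.4.1 and gives a CLR interval that is too narrow whenever participants have more than one PET-positive region and results correlate within participant.

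At ICC 1/3, 122 PET-positive participants and an assumed 1.4 to 2 positive regions on average, coverage is about 89 to 92%, and the lower bound exceeds 0.50 in about 4 to 6% of trials at a true CLR of 0.50. All five regions positive in every positive participant is the extreme, at 80% and 9.7%. At ICC 0.05 to 0.1 with about 1.4 to 2 regions, coverage is about 93 to 95%. With one region each there is no effect.

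Two stronger readings are not supported. A reader might infer that the trial's error rate is inflated. It is not: the success rule in SAP 2.5.2 uses the random-effects interval, and this sentence touches only a supplementary output, and only when no covariate is significant. A reader might also infer that the report would show one quantity with two conflicting intervals. On the literal reading the fallback estimates a marginal proportion and the primary analysis a subject-specific CLR, so the estimates differ in target as well as in width.

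**What to change.** In the last sentence of SAP 2.5.6, change the model named for region-level CLR to the unadjusted logistic random-effects model of Section 2.5.2. Keep plain logistic regression for patient-level PPV only.

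The cost is one phrase. The GLIMMIX code in SAP 5.4.1 already fits this model, so the fallback would repeat the primary CLR result and needs no new programming. The downside is a wider, less favourable supplementary interval than the plain model would give.

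A note in SAP Section 4, saying that the Protocol 12.4.6 model for region-level CLR is a random-effects model, would be tidy but is optional.

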### 2.6 Analysis supporting secondary objectives

The following other secondary efficacy objectives are defined for the EFF unless otherwise specified:

- Evaluate the patient-level sensitivity of [18F]CTT1057
- Evaluate the patient-level specificity of [18F]CTT1057
- Evaluate the patient-level negative predictive value of [18F]CTT1057
- Evaluate the patient-level accuracy of [18F]CTT1057
- Evaluate correct detection rate (CDR)
- Evaluate detection rate
- Evaluate the region level sensitivity of [18F]CTT1057
- Evaluate the region level specificity of [18F]CTT1057
- Evaluate the region level negative predictive value of [18F]CTT1057
- Evaluate the region level accuracy of [18F]CTT1057
- Characterize the safety and tolerability of [18F]CTT1057
- [18F]CTT1057 scan inter-reader variability
- [18F]CTT1057 scan intra-reader variability
- Concordance between [18F]CTT1057 and [68Ga]Ga-PSMA-11 for detection of lesions using central reads
- Evaluate the change in patient management plans attributed to the PET/CT scan
- Assess all the above secondary objectives independently in the subgroup of patients with prior radical prostatectomy (RP) and the subgroup of patients with prior curative intent radiation therapy (RT)

#### 2.6.1 Secondary endpoint(s)

For the following secondary endpoints, centralized imaging assessments (CTS Level 2) will be used as reference standard if pathology assessment (CTS Level 1) is not available for a lesion, inconclusive or negative (for biopsy only).

**Patient-level sensitivity** is defined as the proportion of TP participants among those who are TP or FN

**Patient-level specificity** is defined as the proportion of TN participants among those who are TN or FP

**Patient-level negative predictive value** is defined as the proportion of TN participants among those who are TN or FN

Patient-level accuracy is defined as the proportion of TP and TN participants among all scanned participants (regardless of TP, TN, FP, FN)

**Patient-level correct detection rate** is defined as the proportion of TP participants among all scanned participants (regardless of TP, TN, FP, FN)

**Patient-level detection rate** is defined as the proportion of TP and FP participants among all scanned participants (regardless of TP, TN, FP, FN)

where TP, TN, FP, FN participants are defined as follows:

- PSMA TP participants are those who have at least one TP lesion (with anatomically localized correspondence between [18F]CTT1057 PET imaging and the CTS).
- PSMA TN participants are those who do not show any pathological [F]CTT1057 uptake and will be confirmed as NOT having any lesions with the CTS.
- PSMA FP participants are those who show at least one pathological [18F]CTT1057 uptake but will be verified as NOT having any lesions with the CTS or no lesions are correctly localized in anatomical location by the CTS.
- PSMA FN participants are those who do not show any pathological [18F]CTT1057 uptake but will be confirmed as having at least one lesion with the CTS.

Number of TP, TN, FP, FN participants will be presented and used to calculate the diagnostic performance parameters.

Two-sided exact binomial 95% CIs will be calculated for patient-level diagnostic performance parameters.

[F]CTT1057 scan inter-reader variability is defined as agreement among three readers determinations and will be assessed by Fleiss' Kappa statistic.

[18F]CTT1057 scan intra-reader variability is defined as within-reader agreement for two different time points and will be assessed by Cohen's Kappa statistic. A subset of imaging reading will be performed at two different time points by each reader. See details in imaging charter.

Change in patient management plans attributed to the [18F]CTT1057 PET/CT scan is defined as the percentage of participants who undergo a change in intended treatment plan attributed to

the PET/CT scan as assessed by pre-imaging questionnaire 1 and post-imaging questionnaire 2.

The number and percentage of participants from the F-SAF for each of the following categories of treatment plan in each of the two questionnaires will be calculated: surgery, radiation alone, radiation alone with change in radiation treatment plan (only applicable for questionnaire 2), radiation plus ADT, ADT alone, observation/surveillance, other (free text box).

Treatment plan change is defined as a change in the pair of categories (one category of questionnaire 1, one category of questionnaire 2).

The number and percentage of participants from the F-SAF with treatment plan change as defined above will be calculated. Shift tables comparing treatment plans between questionnaire 1 and 2 will be displayed. The number (%) of participants with and without a change in treatment plans by [18F]CTT1057 local read results (i.e. positive, negative, and inconclusive) will be tabulated.

**Region-level sensitivity** is defined as the proportion of TP regions among those that are TP or FN

**Region-level specificity** is defined as the proportion of TN regions among those that are TN or FP

**Region-level negative predictive value** is defined as the proportion of TN regions among those that are TN or FN

**Region-level accuracy** is defined as the proportion of TP and TN regions among those that are identified on [18F]CTT1057 (regardless of TP, TN, FP, FN)

where TP, TN, FP, FN regions are defined as follows:

- PSMA TP regions are regions containing at least one TP lesion (anatomically localized correspondence between [18F]CTT1057 PET imaging and the CTS).
- PSMA TN regions are regions containing no lesions with pathological [18F]CTT1057 uptake and confirmed by CTS.
- PSMA FP regions are regions containing lesions with pathological [F]CTT1057 uptake but are verified negative by CTS or none is correctly localized in anatomical location by the CTS.
- PSMA FN regions are regions containing no lesions with pathological [F]CTT1057 uptake but are confirmed as having at least one lesion with the CTS.

Number of TP, TN, FP, FN regions will be presented and used to calculate the diagnostic performance parameters.

Two-sided 95% CIs for (overall) region-level diagnostic performance parameters will be calculated using a logistic random-effects models taking into account the correlation among regions within a participant.

For different regions (i.e. prostate region, PLN, extra-pelvic lymph nodes, skeletal, and visceral), two-sided exact binomial 95% CIs for region-level diagnostic performance parameters will be calculated.

Concordance between [18F]CTT1057 and [68Ga]Ga-PSMA-11 for detection of lesions and positive percent agreement will be calculated to assess the concordance.

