Evaluate detection rate	 Proportion of patients who have at least one PET positive lesion, regardless of TP or FP findings, out of all patients who are scanned 		
Evaluate the region level sensitivity of [18F]CTT1057	 Proportion of regions that test positive on both [18F]CTT1057 and CTS (TP) among those regions that are CTS positive (TP or FN) 		
Evaluate the region level specificity of [18F]CTT1057	Proportion of regions that test negative on both [18F]CTT1057 and CTS (TN) among those regions that are CTS negative (FP, or TN)		
Evaluate the region level negative predictive value of [¹⁸ F]CTT1057	Proportion of regions that are CTS and [18F]CTT1057 negative (TN) among those regions that test negative on [18F]CTT1057 (TN or FN)		
Evaluate the region level accuracy of [18F]CTT1057	 Proportion of regions that are CTS and [¹8F]CTT1057 positive (TP) and negative (TN) among those regions that identified on [¹8F]CTT1057 (TP, TN, FP and FN) 		
Evaluate the patient-level positive predictive value related to PSA levels	Percentage of patients who have at least one TP lesion (exactly anatomically localized correspondence between [¹8F]CTT1057 PET imaging and the reference standard), regardless of any co-existent FP findings, out of all patients who are [¹8F]CTT1057 positive, stratified by PSA levels		
Characterize the safety and tolerability of [18F]CTT1057	Incidence of AEs Treatment emergent adverse event (TEAE) rate within 14 days after each PET tracer administration		

Amended Protocol (Version No.	01 Clean)
Allieliaea i Totocoi (VEISION INC	. U i Cicaii)

Objective(s)	Endpoint(s)	
• [¹⁸ F]CTT1057 scan inter-reader variability	Inter-reader agreement of [18F]CTT1057 images	
• [¹⁸ F]CTT1057 scan intra-reader variability	Intra-reader agreement of [18F]CTT1057 images	
 Concordance between [¹⁸F]CTT1057 and [⁶⁸Ga]Ga-PSMA-11 for detection of lesions at lesion level using central reads 	Concordance between [18F]CTT1057 and [68Ga]Ga-PSMA-11 for detection of PSMA-positive lesions (location and number) using central reads	
 Evaluate the change in patient management plans attributed to the PET/CT scan 	Percentage of patients who underwent a change in intended treatment plan attributed to the PET/CT scan as assessed by pre and post imaging questionnaires	

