### 1.2 Study objectives, endpoints and estimands

Table 1-1 Objectives and related endpoints

Objective(s)	Endpoint(s)		
Primary objective(s)	Endpoint(s) for primary objective(s)		
Evaluate the region-level correct localization rate (CLR) of [18F]CTT1057	Proportion of regions containing at least one TP lesion (anatomically localized correspondence between PET imaging and the reference standard), regardless of any coexistent FP findings within the same region, out of all regions containing at least one PET-positive finding by central assessments. See Section 1.2.1 for Primary Estimand		
Evaluate the patient-level positive predictive value (with anatomical localization) of [18F]CTT1057	
 
Proportion of patients who have at least one TP lesion (anatomically localized correspondence between PET imaging and the reference standard), regardless of any co- existent FP findings, out of all patients who are PET/CT scan positive by central assessments.
 
See Section 1.2.1 for Primary Estimand
 
		
Secondary objective(s)	Endpoint(s) for secondary objective(s)		

 
Evaluate the patient-level sensitivity of [18F]CTT1057
 
	
 
Proportion of patients that test positive on [¹8F]CTT1057 and CTS (TP) among those that are CTS positive (TP or FN)
 
		

	ojective(s)	Endpoint(s)			
 		EII			
•	Evaluate the patient-level specificity of [  F]CTT1057	•	Proportion of patients that test negative on [18F]CTT1057 and CTS (TN) among those that are CTS negative (TN or FP)		
•	Evaluate the patient-level negative predictive value of [  F]CTT1057	•	Proportion of patients who are both [18F]CTT1057 and CTS negative (TN) among those who test negative on [18F]CTT1057 (TN or FN)		
•	Evaluate the patient-level accuracy of [18F]CTT1057	•	Proportion of patients that are CTS and [18F]CTT1057 positive (TP) and negative (TN) among those patients that identified on [18F]CTT1057 (TP, TN, FP or FN)		
•	Evaluate correct detection rate (CDR)	•	Proportion of patients who have at least one TP lesion (exactly localized correspondence between PET imaging and the reference standard), regardless of any co-existent FP findings, out of all patients who are scanned		
•	Evaluate detection rate	•	Proportion of patients who have at least one PET positive lesion, regardless of TP or FP findings, out of all patients who are scanned		

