#### 2.2 Analysis sets

The Full Analysis Set (FAS) includes all randomized participants.

The Efficacy Analysis Set (EFF) includes all randomized participants who receive the dose of investigational treatment (i.e. [18F]CTT1057), have both an evaluable [18F]CTT1057 PET/CT scan imaging and at least one evaluable CTS assessment, and have not received any prohibited systemic antineoplastic therapy before the completion of PET/CTs and CTS procedures.

The [18F]CTT1057 Safety Set (F-SAF) includes all participants who received the investigational treatment (i.e. [18F]CTT1057).

The [68Ga]Ga-PSMA-11 Safety Set (Ga-SAF) includes all participants who received [68Ga]Ga-PSMA-11. Participants will be analyzed according to the study treatment received.

The **Safety Set (SAF)** includes all participants who received at least one of [F]CTT1057 or [Ga]Ga-PSMA-11.

The number (%) of participants in each analysis set will be summarized and information about analysis sets for each participant will be displayed in a listing.

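### Detection rate and CDR are defined over all scanned participants but analysed in the EFF, so the reported rates can differ from their definitions

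*SAP*

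**What the plan says.** **Denominator.** SAP 2.6.1 says that CDR "is defined as the proportion of TP participants among all scanned participants (regardless of TP, TN, FP, FN"), and that detection rate "is defined as the proportion of TP and FP participants among all scanned participants (regardless of TP, TN, FP, FN"). It defines patient-level accuracy over the same group. SAP Table 1-1 gives detection rate as "Proportion of patients who have at least one PET positive lesion, regardless of TP or FP findings, out of all patients who are scanned", and ends its CDR definition with "regardless of any co-existent FP findings, out of all patients who are scanned". Protocol Table 2-1 and Protocol 12.5.1 also use the scanned participants.

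**Analysis set.** SAP 2.6 states: "The following other secondary efficacy objectives are defined for the EFF unless otherwise specified". Detection rate, CDR and accuracy are in the list that follows, and no other set is named for them. Under SAP 2.2, EFF members must have received [18F]CTT1057 and must "have both an evaluable [18F]CTT1057 PET/CT scan imaging and at least one evaluable CTS assessment, and have not received any prohibited systemic antineoplastic therapy" until both PET scans and the CTS work-up are complete.

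**Related rules.** SAP 2.6.3 removes from secondary efficacy analyses only those who were injected but did not undergo or complete the scan. The F-SAF is named for reader agreement, tracer concordance and change in management (SAP 2.6.1 and 2.6.2). SAP Section 4, on changes to the protocol's analyses, does not mention a narrower denominator for these rates.

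**The concern.** A scanned participant can fall outside the EFF by lacking an evaluable CTS result or by starting prohibited systemic therapy too early. The definitions keep that participant in the denominator and the analysis set removes him. A third group, those scanned with a non-evaluable image, is also removed, and the text does not say whether they count as scanned.

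For detection rate, the Table 1-1 definition asks only whether there is a PET-positive lesion, true or false. No CTS result is needed, so a missing one is no reason to exclude anybody.

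For CDR, SAP 1.2.1 contrasts it with PPV as the unconditional proportion of true positives in the whole population. Removing unverified participants moves it away from that description.

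The early-therapy exclusion may also depend on the scan result. The local [18F]CTT1057 report goes to the treating physician, and the management options in Protocol Appendix 4 include ADT. At stake is how two descriptive secondary rates are read; no success criterion is involved.

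**Working it through.** **1. The plan's own figure.** No planned value is stated for CDR. The only calculation that uses the detection rate is the PPV sample size (SAP 3.1). An exact one-sided binomial test with p0 = 0.20 and p1 = 0.33 needs 122 PET-positive participants: success at 34 or more true positives, type I error 0.0228, power 0.905. Then 122/0.80 = 152.5 (the plan has 152), and 152/(1 − 0.20) = 190. The plan's figures reproduce and are not affected by this point.

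**2. Inputs.**
- EFF size 152 and enrolment 190 (SAP Section 3)
- Detection rate 0.80, and PPV 0.33 under the alternative (SAP 3.1)
- k, the number scanned but outside the EFF: not given in the documents. I take 0 to 38 as an assumed range, since 190 − 152 = 38.

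In the EFF, PET-positive = 152 × 0.80 = 121.6, TP = 121.6 × 0.33 = 40.1, and CDR = 40.1/152 = 26.4%.

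**3. All k lack CTS.** None can be classified TP, so CDR over all scanned = 40.1/(152 + k).

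| k | CDR over all scanned | EFF value higher by |
|---|---|---|
| 5 | 40.1/157 = 25.6% | 0.8 points |
| 10 | 40.1/162 = 24.8% | 1.6 points |
| 19 | 40.1/171 = 23.5% | 2.9 points |
| 38 | 40.1/190 = 21.1% | 5.3 points |

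The relative reduction is k/(152 + k) whatever the PPV: 3.2% at k = 5, 6.2% at k = 10 and 20% at k = 38.

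**4. All k excluded for early therapy, with a CTS result.** If a share t of them are TP, CDR over all scanned = (40.1 + k·t)/(152 + k). At k = 10:
- t = 0: 24.8%
- t = 0.264: 26.4% (break-even)
- t = 0.5: 45.1/162 = 27.9%
- t = 1: 50.1/162 = 30.9%

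The EFF figure can be too high, equal or too low.

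**5. Detection rate.** With positivity s among the k, the rate over all scanned = (121.6 + k·s)/(152 + k). At k = 10 it runs from 121.6/162 = 75.1% (s = 0) to 131.6/162 = 81.2% (s = 1). At k = 38 it runs from 64.0% to 84.0%. At s = 0.80 it does not move.

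**The case against.** The strongest defence is that scanned, in SAP 2.6.1, means scanned and classified. That section builds the rates from counts of TP, TN, FP and FN, all of which need a CTS result, and SAP Section 3 calls the same 152 people evaluable in one place and scanned in another. This reading is possible, but it is not written down. It also cannot explain a CTS requirement for detection rate as Table 1-1 defines it.

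Several counterpoints stand:
- k is probably small. [68Ga]Ga-PSMA-11 PET and contrast CT (or MRI) are mandatory, one evaluable CTS assessment suffices, and imaging done before consent can count. ADT is prohibited until the CTS work-up is complete, so early-therapy exclusions should be deviations. The 20% dropout allowance also covers people never scanned.
- Counting unverified participants as not TP is a worst-case rule and sits awkwardly with SAP 2.6.4, which imputes nothing. It gives a conservative bound rather than the only right CDR.
- A CTS read after ADT may be affected by lesion shrinkage, which Amendment 01 gives as the reason for the prohibition.
- The reader-agreement tables in the F-SAF already hold positive and negative reads for every evaluable scan, and analysis-set membership is listed. The gap is traceable, although no detection rate is planned from those tables.
- Neither rate has a threshold or hypothesis.

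A reader might infer that CDR in the EFF becomes conditional in the way PPV is. It does not: PET-negative participants stay in its denominator.

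**Conclusion.** The mismatch between definition and analysis set is real for detection rate and CDR, and the denominator for accuracy needs the same clarification. If k scanned participants lack CTS, the EFF overstates CDR by 0.8 points at k = 5 and 1.6 at k = 10. The limit is 5.3 points at k = 38. These figures rest on 152 in the EFF, 80% positivity and PPV 0.33; k is an assumption.

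Two stronger readings are tempting. One is that CDR is inflated overall. That follows only for unverified scans. If early therapy tends to follow a positive scan, that exclusion could lower CDR, and the net direction is unknown. The other is that detection rate shifts by a predictable amount. The documents give neither k nor the positivity of those excluded, so neither size nor direction is fixed. This is a minor point of specification, with no effect on the co-primary endpoints or the sample size.

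**What to change.** Amend SAP 2.6 and 2.6.1 as follows:
- **Detection rate:** compute by central reader in all F-SAF participants with an evaluable [18F]CTT1057 scan, whether or not a CTS result exists.
- **CDR:** report on that same denominator, keeping any available CTS classification and counting unverified participants as not TP. Label it a conservative lower-bound figure, place it beside the EFF value, and state that the EFF value is restricted to verified participants.
- **Accuracy:** state its denominator.
- **Accounting:** report the number scanned but outside the EFF by reason (no evaluable CTS, early prohibited therapy, non-evaluable image).

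The cost is a short SAP edit, one extra display and a CDR that may look slightly less favourable. The data are already collected.
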